2.3.3 ASSESSMENT OF POTENTIAL RISKS AND BENEFITS

This trial protocol incorporates numerous design elements to minimize risk to participants to meet human participant protection requirement. The dose of NR in this trial is comparable to the dose used in other published and ongoing clinical trials to increase blood NAD+ levels and have shown minimal to mild side effects. The duration of treatment in this trial of 10 days is significantly shorter than that of many published clinical trials with NR to reduce risk but likely sufficient to observe benefit. To further mitigate risk, we will exclude participants with concomitant niacin, nicotinamide, or NR supplementation.

The safety profile of NR has been reported in several small-scale randomized and nonrandomized clinical trials involving heathy volunteers. Most of these reported risks are mild in a grading scale (see section 2.3.1). Based on prior data in healthy populations, obese participants and in those with AKI, there have been no reported major adverse events. Minor adverse events include gastrointestinal side effects, muscle and back pains. It remains possible that NR in patients with COVID-19 could have unexpected effects or make COVID-19 complications worse. The potential benefit would be less kidney injury and preservation of kidney function to reduce the degree of CKD in patients with COVID-19 infection. Taking into account the preliminary data available on the possible benefit of NR to boost NAD+ levels for kidney protection along with the relative lack of therapeutic options for AKI incidence and severity it appears to reasonably balance potential risks with possible benefit that may outweigh such risks. By appropriate daily clinical evaluation, laboratory monitoring, soliciting of symptoms and incident reporting by participants during the study, the risk to participants will be minimized.

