3 OBJECTIVES AND ENDPOINTS

OBJECTIVES	ENDPOINTS	JUSTIFICATION FOR		
		ENDPOINTS		
Primary				
 To determine the effect of nicotinamide riboside (NR) on whole blood NAD+ levels in hospitalized patients with COVID-19 infection and AKI during the 10-day intervention period; To evaluate the safety of NR in patients with COVID-19 infection and AKI during the 10-day intervention period. 	 The primary endpoint is the rate of change in whole blood NAD+ level over the 10 day period from baseline to day 10. Safety of NR in hospitalized patients with COVID-19 and AKI (defined as the occurrence of at least one serious adverse event of grade 3 or higher or the occurrence of thrombocytopenia defined as >25% decline in blood platelet count from baseline. 	 Recent clinical data indicate a reduction of blood NAD+ level in AKI patients and an increase in NAD+ in 48 hrs with NR treatment; The safety of NR in COVID-19 patients is not known 		
Secondary	-	-		
• To determine the effect of	• The rate of change in AUC	• The recovery of AKI, as		
NR on changes in AUC	benchmarked to baseline;	assessed by AUC serum		

Table 2: Study objectives, endpoints, and justification for endpoints

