8.3.4 TIME PERIOD AND FREQUENCY FOR EVENT ASSESSMENT AND FOLLOW-UP

The study investigators will assess and record all events with start dates occurring any time after informed consent is obtained until Day 90 – the last visit. The study investigator will review EHR daily to collect and assess all AEs (including SAEs) from the time participants provided consent to the study until Day 10 and again during Day 30 and Day 90 follow-up visits regardless of its relationship to study drug. At each visit, the investigator will inquire about the occurrence of any new and the prognosis of already documented AE/SAEs since the last visit. All AEs will be captured in detail and followed to satisfactory resolution or stabilization, until the investigator deems the event chronic or not clinically significant and until the participant is considered to be stable. The participants will receive standard of care for the events. Site investigators will also assess if there is a reasonable possibility that the study drug or procedure caused the event. Investigators will also consider if the event is explained by the participant's underlying medical conditions, anticipated clinical course, previous medical conditions, and concomitant medications.

Routine and safety laboratory values from the respective hospital laboratories will be reported by each site investigator to the SAC as soon as the results are available to the study database. Participants will receive standard of care for the event and followed to satisfactory resolution or stabilization, The DCC will review laboratory results for completeness. Any abnormal laboratory test results (clinical chemistry, hematology, or urinalysis) or other safety assessment (e.g., CPK), including those that worsen from the baseline, felt to be clinically significant in the medical and scientific judgement of the investigator, will be recorded as AEs. The SAC will review AEs weekly and SAEs on a daily basis and any events that the clinical centers categorize as requiring treatment discontinuation for safety reasons.

The following laboratory results will be flagged as expected study AEs in this trial:

- Thrombocytopenia: Platelet count >25% reduction from the baseline;
- Liver function test abnormalities: AST, ALT, total bilirubin, alkaline phosphatase > 4 times the upper limit of normal;
- Creatinine phosphokinase (CPK): > 4 times upper limit of normal;

The following symptoms will be flagged as expected study AEs in this trial:

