8.3.5 ADVERSE EVENT REPORTING

Information on all AEs will be recorded on the appropriate eCRF. All related and relevant signs, symptoms, and results of diagnostic procedures performed because of an AE will be grouped together and recorded as a single diagnosis. AEs and SAEs related to COVID-19 outcomes or expected AEs with NR or study procedures will not be reported to sIRB and not adjudicated by SAC. Any baseline medical condition and laboratory results that are present at the time that the participant consented to the study but do not deteriorate will not be reported as an AE. However, if the medical condition deteriorates and any laboratory results become abnormal at any time during the study, these will be reported as AEs. Unexpected AEs and their relatedness to study drug or procedure will be reported.

Aggregate analyses of adverse events observed from the NIRAVA trial will detail new information regarding the investigational product NR (i.e. new side effects or increasing frequency of side effects) will be reported to SAC on weekly basis. Significant non-clinical findings will also be reported to SAC if they are suggestive of increased risk for study patricians.

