Study-specific outcomes of COVID-19 infection and critical illness will be systematically collected for all participants in both study group and are exempt from adverse event reporting unless the investigator considers the event to be Definitely or Possibly Related (or of an Uncertain Relationship – section 8.3.3.2) to the study drug or study procedures. Examples of study-specific clinical outcomes include:

- Death not related to the study procedures
- Cardiovascular events
 - Receipt of vasopressors
 - Atrial or ventricular arrhythmia
 - Cardiac arrest
 - Respiratory events
 - Hypoxemia requiring supplemental oxygen
 - o Acute respiratory distress syndrome
 - Receipt of mechanical ventilation
 - Receipt of extra-corporeal membrane oxygenation
- Gastrointestinal events
 - Elevation of aspartate aminotransferase or alanine aminotransferase
 - Acute pancreatitis
 - Severe diarrhea
- Hematological events
 - o Anemia

o Thrombocytopenia

Note: A study-specific clinical outcome may also qualify as a reportable adverse event.

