Potential participants who may have severe AKI or advanced CKD will be considered with a binary independent variable in the models addressing this condition with corresponding displays of the line and whisker plots by treatment group and summary tables of coefficients, standard errors and p-values. Interactions between this binary variable and treatment will be of interest and will be described.

Capture and tabulation of concomitant medications, dialysis, co-enrollment in another COVID-19 clinical trial, any new standard of care, pre-existing CKD, and treatments by study arm (NR, Placebo) may be used to define other potential adjustments with binary or categorical variables to be defined post hoc in exploratory analyses. Such models may motivate extended interpretations of any treatment effects found.

PRIMARY END POINT: Safety

All reportable AEs will be listed by Preferred Term by subject, treatment, clinical site, grade, relation to treatment, severity, and seriousness. All unanticipated events will be listed by treatment and clinical site with a detailed description of each event, incident, experience or outcome. An unblinded statistician will summarize safety data periodically for the DSMB.

AEs will be tabulated by treatment and clinical site, displaying, for each event, the number and percentage of participants experiencing at least one Grade 3 or 4 occurrence and he null hypothesis to be tested is H_0 : $p_{NR}=p_{Placebo}$ where p_{NR} and $p_{Placebo}$ are the probabilities of experiencing at least one Grade 3 or Grade 3 event in the NR and Placebo groups. H_0 will be tested with Fisher's Exact test, overall and by clinical site. Additionally, treatment groups will be contrasted on the occurrence at least once of each event with Fisher's exact test. All statistical testing will be two-sided with a significance level of 5%.

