Adverse Events and Serious Adverse Events: Reportable AEs will be entered into the REDCap study database. Reportable AEs will be entered, classified, and graded according to the most current versions of the CTCAE by the site investigator and independent site SAC Physician. Adverse events indicated as Serious Adverse Events will result in real-time alerts through the REDCap system to support expedited reporting. Entry of reportable Adverse Events will trigger notification to the independent SAC physician to initiate the independent review and adjudication process as described in section 8.3.7. AEs will be coded at the DCC using the MedDRA controlled terminology.

Biosample Inventory and Tracking: The REDCap study database will include screens at each visit for sites to report samples obtained and shipped to the UTHSA COVID-19 Repository. Sample tracking will trigger notification to the repository. Samples received will be reconciled with REDCap biosample tracking on the day of receipt. Data status reports will flag expected and missing sample tracking data.

Data Status Reports: Enrollment data will be entered into REDCap on the day of enrollment. Enrollment entry enables tracking and management of participant data and samples and will trigger notification to the site and DCC study team. Data entry will be entered every day during the 10-day treatment period and within one week of follow-up visits. Late data will be listed on an exception report by site and by participant. Similarly, data discrepancies will be resolved within a week of firing. Late data discrepancy resolutions will be listed on an exception report by site and by patient. Data will be reviewed by the DCC within 24 hours of complete entry. The site investigator will be responsible for review of data collection tools and processes, and review of data and reports.

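### The protocol contradicts itself on whether COVID-19 and critical-illness outcomes exempt from adverse event reporting count toward the co-primary safety endpoint

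*Combined protocol and SAP*

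**What the plan says.** **The endpoint.** Section 1.1 and Table 2 in section 3 give safety as a primary endpoint, "defined as the occurrence of at least one serious adverse event of grade 3 or higher" or a platelet decline of more than 25% from baseline. Neither requires the event to be related, unexpected or reportable.

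**Sections that record everything.**
- 2.3.3 and 8.2: all AEs go into the study database and onto the AE form.
- 8.3.1: all Grade 3 and 4 AEs are captured.
- 8.3.2: death and life-threatening events are SAEs, and every SAE goes on the SAE form.
- 8.3.4: AEs and SAEs are collected "regardless of its relationship to study drug".
- 8.3.5 (opening sentence) and the clinical-data paragraph of 10.1.8.1 are to the same effect.

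**Sections that filter.**
- 8.3.6: a list of outcomes of COVID-19 and critical illness (death not related to study procedures, vasopressors, arrhythmia, cardiac arrest, ARDS, ventilation, ECMO and others) "are exempt from adverse event reporting unless the investigator considers the event to be Definitely or Possibly Related", "or of an Uncertain Relationship". The same paragraph says that these outcomes are collected systematically in both arms. A closing note says that one of them may also be a reportable AE, without saying when.
- 8.3.5: COVID-19 outcomes and "expected AEs with NR or study procedures will not be reported to sIRB and not adjudicated by SAC".
- 8.2: investigators decide which AEs are reportable.
- 10.1.8.1: "Reportable AEs will be entered into the REDCap study database".
- 9.4.2, safety: "All reportable AEs will be listed by Preferred Term by subject, treatment, clinical site, grade, relation to treatment, severity, and seriousness". The text then tabulates AEs and tests, by Fisher's exact test, the proportion with at least one Grade 3 or 4 event.

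**The concern.** Whether a COVID-19 complication in one blinded participant was caused by nicotinamide riboside (NR) can rarely be judged. Section 8.3.3.2 makes an event probably not related when the clinical state can reasonably explain it, and that description fits most arrests, intubations and deaths in this population. Section 2.3.3 accepts that NR "could have unexpected effects or make COVID-19 complications worse". Harm of that kind would show as an imbalance between arms, not as a series of events judged related.

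If relatedness decides which events enter the analysis, the Fisher test in 9.4.2 and the interim harm test in 9.4.6 can miss that imbalance. The result matters for the programme, because absence of a significant increase in harm is a condition of all three scenarios in section 2.1 for going on to Phase IIb or Phase III. Sites could also read the rules differently, and the endpoint would then be ascertained unevenly.

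**Working it through.** **1. One participant traced through the text.** Take a participant ventilated on Day 4 who dies on Day 7, with both events judged probably not related.
- Under sections 3, 8.3.1, 8.3.2 and 8.3.4, both events are recorded and the participant meets the endpoint.
- Under 8.3.6, followed by the reportable-AE wording in 10.1.8.1 and 9.4.2, neither event need become an AE record and the participant may count as event-free.
- Nothing in 9.4.2 or 9.4.6 chooses between these routes, or draws on the separately collected outcomes.

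**2. A gap that does not depend on the exemption.** Section 8.3.3.1 grades death as 5. The 9.4.2 tabulation and test name Grade 3 or 4 (the hypothesis repeats Grade 3), and they leave out the platelet component. Sections 1.1, 3 and 9.4.6 say grade 3 or higher. Taken literally, the 9.4.2 test omits deaths as such.

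**3. Size, as an illustration.** The documents give no event rate or power for the safety endpoint, so there is no planned figure to reproduce.

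Inputs from the documents: 100 randomized (5.5) at 1:1 (6.1.1), so 50 per arm; two-sided Fisher test at 5% (9.4.2); 120 deaths among 1,213 patients, 120/1213 = 9.9% (2.2).

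Assumptions: another qualifying event in r = 10% of each arm; exempt-type events in q of each arm, independent of the others; a share s of exempt events judged related or uncertain, and so still counted.

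Counted rate per arm = 1 − (1 − r)(1 − s·q). Power is exact: the binomial probability, summed over all pairs of counts, of p ≤ 0.05 with more events on NR.

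| Exempt events, placebo → NR | Share counted (s) | Counted rates | Power to show harm |
|---|---|---|---|
| 20% → 40% | all | 1 − 0.9×0.8 = 28.0% vs 1 − 0.9×0.6 = 46.0% | 0.386 |
| 20% → 40% | one quarter | 1 − 0.9×0.95 = 14.5% vs 1 − 0.9×0.90 = 19.0% | 0.051 |
| 20% → 40% | none | 10% vs 10% | 0.009 |
| 9.9% → 19.8% | all | 1 − 0.9×0.901 = 18.9% vs 1 − 0.9×0.802 = 27.8% | 0.130 |
| 9.9% → 19.8% | one quarter | 12.2% vs 14.5% | 0.025 |
| 9.9% → 19.8% | none | 10% vs 10% | 0.009 |

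With r between 5% and 20%, the 20% → 40% case gives 31–44% if all are counted, 4–6% with a quarter and 0.4–1.4% with none. The 9.9% → 19.8% case gives 9–16%, 2–3% and 0.4–1.4%.

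**The case against.** The strongest reply is that the exemption concerns reporting, not analysis. It sits in a reporting section, the endpoint definitions carry no such condition, and many sections require every AE and SAE to be recorded. In 9.4.2 the word reportable is attached to the listing, while the sentence leading to the test speaks simply of AEs. The exemption also keeps events of uncertain relationship, and its closing note lets an exempt outcome be reportable. All of this stands. It means that exclusion is one reading and not a stated rule, but it does not settle which reading a site or programmer should follow.

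A reader might infer three stronger things that the documents do not support.
- **That thrombocytopenia is lost from the endpoint.** The fall of more than 25% is a separate component, and it can be derived from the daily platelet counts in Table 4 whatever is reported as an AE.
- **That the Safety Adjudication Committee (SAC) can no longer detect a pattern.** Section 8.3.5 removes adjudication of COVID-related events. But 8.3.4 has the committee review AEs weekly and SAEs daily, 8.3.5 sends it weekly aggregate analyses, and 8.3.6 has the DSMB review clinical outcomes.
- **That about ten deaths would fall outside the endpoint.** The 9.9% has no time window, and section 2.2 says that the dates of death are unknown.

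Death is also compared by arm in the ordinal and MAKE (major adverse kidney events) analyses. Those are secondary efficacy endpoints, though. They do not include ventilation, arrest or ARDS, and they do not feed the harm boundary.

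**Conclusion.** The concern holds as an unresolved contradiction over which events enter a co-primary endpoint. It does not show that the plan chose to exclude deaths or ventilation, although a reader could take 8.3.6 that way.

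If the filtering reading were applied, harm acting through worse COVID-19 would be nearly invisible to the safety test: in the 20% to 40% case, power falls from 39% to about 5% or to under 1%. These sizes rest on assumed rates and on the share of events judged related or uncertain. Larger assumed effects give more striking contrasts (20% to 50%: 0.739 against 0.009), but no section supports a rise of that size. Counting everything does not make the test strong either. For 9.9% to 19.8% it reaches only 13%, against under 1% if no exempt event is counted. The case for change is that the endpoint should measure what section 3 says it measures. The contradiction should be resolved before any interim or final safety analysis.

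**What to change.** - **9.4.2 and 9.4.6:** state that the safety endpoint is derived from all collected serious events of grade 3 to 5, including the outcomes listed in 8.3.6 and all deaths, plus the platelet component from laboratory data, regardless of relatedness, expectedness or reportability. Correct the Grade 3 or 4 wording and add the platelet component to the 9.4.2 test. The platelet definition in 9.4.6 (below 50,000 per microliter) differs from that in section 3 and must be reconciled with it.
- **8.3.5 and 8.3.6:** state that the exemption covers expedited reporting and adjudication only.
- **9.4.2 and 10.1.8.1:** replace reportable AEs with all recorded AEs and study-specific outcomes.
- **DSMB reports:** give counts of these outcomes by arm.

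The cost is protocol and analysis wording and one derived variable, because 8.3.6 already requires the outcomes to be collected. The drawback is a higher background event rate in both arms, which dilutes an effect confined to other events. A table of exempt and other events by arm would show where any difference lies.

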8.3.7 EVENT ADJUDICATION PROCESS

Unexpected AEs and SAEs occurring from the time the informed consent signed through the Day 90 visit will be documented, recorded, and reported. Upon entry into REDCap eCRF, a notification will be generated to the independent site SAC member that unexpected AEs are ready for review. SAC members will be expected to review unexpected AEs within one week of notification. (Unexpected SAEs will have different language in the text and will require same day review by the SAC member.) SAC review will be separate from the expedited SAE reporting process and incomplete SAC assessment will in no way delay expedited SAE reporting.

Adjudicators will be blinded to the study treatment actually given to each patient and will use subject matter knowledge to render opinions regarding, for example, relatedness to treatment. The database will be configured so that certain baseline data will be viewable, including age, race, gender, BMI, diabetic status (diabetic, not diabetic), and current smoking status (smoker, not a smoker).

The REDCap adjudication module will compare the site investigator's AE grade and relatedness with that of the independent site SAC Physician. Where they agree, no further action will be needed and the AE will be submitted to statistician for reports to DSMB. Where the independent site SAC Physician disagrees with site investigator's AE grade and relatedness, the site investigator will be notified to review the report. Where the site investigator and independent SAC member agree, AEs that are not also other reportable events will be considered complete. AEs meeting the definition of other reportable events such as SAEs will trigger those processes with automated system notifications. Where the site investigator and independent SAC member disagree, the AE will be labeled as needing adjudications. Weekly adjudication meetings will be held if there are unexpected AEs needing adjudication. The study investigator will work collaboratively with the SAC on adjudication calls to make a final determination if an adverse event or reaction has a reasonable possibility of having been caused by the study drug or procedure as outlined in 21 CFR 312.32(a)(1). The protocol for handling of unexpected AEs and SAEs which are not uniformly adjudicated will be established. Any change to an adjudicated AE by a site investigator or SAC member will trigger review by the safety desk for impact on the adjudication. Where changes impact the adjudication decision, the event will be triggered for readjudication by the safety desk. The Adjudication process will be tracked and managed by DCC staff filling the Safety Desk role. AEs will be summarized for the DSMB as described in the DSMB plan.

8.3.8 REPORTING EVENTS TO PARTICIPANTS

Information regarding this clinical trial will be available on ClinicalTrials.gov. The study investigators will notify SAC, sIRB, DSMB, and FDA if new safety information regarding the nutritional supplement becomes available from ChromaDex and any published literature during the implementation of the study within three calendar days of obtaining the information. Study investigators will follow DSMB recommendation regarding how quickly the information is to be disseminated to participants.

